**Table B      Serial Sample Breakdown**

Cycle	Study Day	Time	Window	PK	Immunogenicity
Cycle 1	Day 1	Predose	Within 2 hr	x	x
		10 min after the end of brentuximab vedotin infusion	±5 min	x	
		4 hr after the end of brentuximab vedotin infusion	±30 min	x	
	Day 2	24 hr after the end of brentuximab vedotin infusion	±1 hr	x	
	Day 3	48 hr after the end of brentuximab vedotin infusion	±2 hr	x	
	Day 4	72 hr after the end of brentuximab vedotin infusion	±2 hr	x	
	Day 8	168 hr after the end of brentuximab vedotin infusion	±3 hr	x	
	Day 11	240 hr after the end of brentuximab vedotin infusion	±3 hr	x	
	Day 15	336 hr after the end of brentuximab vedotin infusion	±3 hr	x	
Cycle 2	Day 1	Predose	Within 2 hr	x	x
		10 min after the end of brentuximab vedotin infusion	±5 min	x	
		4 hr after the end of brentuximab vedotin infusion	±30 min	x	
	Day 2	24 hr after the end of brentuximab vedotin infusion	±1 hr	x	
	Day 4	72 hr after the end of brentuximab vedotin infusion	±2 hr	x	
	Day 8	168 hr after the end of brentuximab vedotin infusion	±3 hr	x	
Cycle 3 and subsequent cycles	Day 1	Predose	Within 2 hr	x a	x a
		10 min after the end of brentuximab vedotin infusion	±5 min	x a	
–	Safety follow-up			x	x

(a) To be performed every 2 cycles after Cycle 3 and subsequent cycles.

## **Appendix B Responsibilities of the Investigator**

Clinical research studies sponsored by the sponsor are subject to ICH GCP and all the applicable local laws and regulations.

The investigator agrees to assume the following responsibilities:

1. Conduct the study in accordance with the protocol.
2. Personally conduct or supervise the staff who will assist in the protocol.
3. Ensure that study-related procedures, including study specific (non routine/non standard panel) screening assessments are NOT performed on potential subjects, before the receipt of written approval from relevant governing bodies/authorities.
4. Ensure that all colleagues and employees assisting in the conduct of the study are informed of these obligations.
5. Secure prior approval of the study and any changes by an appropriate IRB/IEC that conform to ICH, and local regulatory requirements.
6. Ensure that the IRB/IEC will be responsible for initial review, continuing review, and approval of the protocol. Promptly report to the IRB/IEC all changes in research activity and all anticipated risks to subjects. Make at least yearly reports on the progress of the study to the IRB/IEC, and issue a final report within 3 months of study completion.
7. Ensure that requirements for informed consent, as outlined in ICH and local regulations, are met.
8. Obtain valid informed consent from each subject who participates in the study, and document the date of consent in the subject's medical chart. Valid informed consent is the most current version approved by the IRB/IEC. Each ICF should contain a subject authorization section that describes the uses and disclosures of a subject's personal information (including personal health information) that will take place in connection with the study. If an ICF does not include such a subject authorization, then the investigator must obtain a separate subject authorization form from each subject or the subject's legally acceptable representative.
9. Prepare and maintain adequate case histories of all persons entered into the study, including eCRFs, hospital records, laboratory results, etc, and maintain these data for a minimum of 2 years following notification by the sponsor that all investigations have been discontinued or that the regulatory authority has approved the marketing application. The investigator should contact and receive written approval from the sponsor before disposing of any such documents.
10. Allow possible inspection and copying by the regulatory authority of GCP-specified essential documents.
11. Maintain current records of the receipt, administration, and disposition of sponsor-supplied drugs, and return all unused sponsor-supplied drugs to the sponsor.

**CONFIDENTIAL**

12. Report adverse reactions to the sponsor promptly. In the event of an SAE, notify the sponsor within 24 hours.

## **Appendix C Investigator Consent to Use of Personal Information**

Takeda will collect and retain personal information of investigator, including his or her name, address, and other personally identifiable information. In addition, investigator's personal information may be transferred to other parties located in countries throughout the world (eg, the United Kingdom, United States, and Japan), including the following:

- Takeda, its affiliates, and licensing partners.
- Business partners assisting Takeda, its affiliates, and licensing partners.
- Regulatory agencies and other health authorities.
- IRBs and IECs.

Investigator's personal information may be retained, processed, and transferred by Takeda and these other parties for research purposes including the following:

- Assessment of the suitability of investigator for the study and/or other clinical studies.
- Management, monitoring, inspection, and audit of the study.
- Analysis, review, and verification of the study results.
- Safety reporting and pharmacovigilance relating to the study.
- Preparation and submission of regulatory filings, correspondence, and communications to regulatory agencies relating to the study.
- Preparation and submission of regulatory filings, correspondence, and communications to regulatory agencies relating to other medications used in other clinical studies that may contain the same chemical compound present in the study medication.
- Inspections and investigations by regulatory authorities relating to the study.
- Self-inspection and internal audit within Takeda, its affiliates, and licensing partners.
- Archiving and audit of study records.
- Posting investigator site contact information, study details and results on publicly accessible clinical trial registries, databases, and websites.

Investigator's personal information may be transferred to other countries that do not have data protection laws that offer the same level of protection as data protection laws in investigator's own country.

Investigator acknowledges and consents to the use of his or her personal information by Takeda and other parties for the purposes described above.

## **Appendix D ECOG Scale for Performance Status**

Grade	Description
0	Normal activity. Fully active, able to carry on all predisease performance without restriction.
1	Symptoms but ambulatory. Restricted in physically strenuous activity, but ambulatory and able to carry out work of a light or sedentary nature (eg, light housework, office work).
2	In bed <50% of the time. Ambulatory and capable of all self-care, but unable to carry out any work activities. Up and about more than 50% of waking hours.
3	In bed > 50% of the time. Capable of only limited self-care, confined to bed or chair more than 50% of waking hours.
4	100% bedridden. Completely disabled. Cannot carry on any self-care. Totally confined to bed or chair.
5	Dead

Source: Oken MM, Creech RH, Tormey DC, Horton J, Davis TE, McFadden ET, et al. Toxicity and response criteria of the Eastern Cooperative Oncology Group. American Journal of Clinical Oncology 1982;5(6):649-55.

## **Appendix E New York Heart Association Functional Classification**

- Class I No limitation of physical activity. Ordinary physical activity does not cause undue fatigue, palpitation or dyspnea.
- Class II Slight limitation of physical activity. Comfortable at rest, but ordinary physical activity results in fatigue, palpitation or dyspnea.
- Class III Marked limitation of physical activity. Comfortable at rest, but less than ordinary activity causes fatigue, palpitation or dyspnea.
- Class IV Unable to carry out any physical activity without discomfort. Symptoms of cardiac insufficiency may be present even at rest. If any physical activity is undertaken, discomfort is increased.

SGN-35\_C25010\_Protocol\_Original

### 3.0 LIST OF ABBREVIATIONS

ADC	antibody-drug conjugate
AE	adverse event
ALCL	anaplastic large cell lymphoma
ALT	alanine aminotransferase
AST	aspartate aminotransferase
ATA	antitherapeutic antibodies
ATC	Anatomical Therapeutic Chemical classification
AUC	area under the concentration-time curve
CI	confidence interval
CL	clearance
C max	maximum observed concentration
CR	complete response
CSR	clinical study report
CT	computed tomography
CTMS	clinical trial management system
CV	coefficient of variation
DCR	Disease control rate
DO.R	duration of response
ECG	Electrocardiogram
ECOG	Eastern Cooperative Oncology Group
eCRF	electronic case report form
EOT	end of treatment
HL	Hodgkin lymphoma
IRF	independent review facility
MedDRA	Medical Dictionary for Regulatory Activities
miITT	modified intent-to-treat
MMAE	monomethylauristatin E
nATA	neutralizing antitherapeutic antibodies
NCI CTCAE	National Cancer Institute Common Terminology Criteria for Adverse Events
ORR	overall response rate
OS	overall survival
PD	progressive disease
PET	positron emission tomography
PFS	progression-free survival
PK	pharmacokinetic(s)
PR	partial response
RDI	relative dose intensity
SAE	serious adverse event
sALCL	systemic anaplastic large cell lymphoma
SAP	statistical analysis plan

---

SD	stable disease
SPD	sum of products of diameters
StdDev	standard deviation
SMQ	standardised MedDRA queries
Tab	total antibody
TEAE	treatment-emergent adverse event
$t_{\max}$	time of first occurrence of $C_{\max}$
WHO	World Health Organization

## 4.0 OBJECTIVES

### 4.1 Primary Objectives

The primary objective is to evaluate the efficacy and the safety of brentuximab vedotin in Chinese patients with relapsed/refractory CD30+ HL or sALCL.

### 4.2 Secondary Objectives

The secondary objective is to evaluate the PK and immunogenicity of brentuximab vedotin in Chinese patients with relapsed/refractory CD30+ HL or sALCL.

### 4.3 Additional Objectives

Not applicable.

### 4.4 Study Design

This is a single-arm, open-label, multicenter, phase 2 study designed to evaluate the efficacy, safety, and PK of brentuximab vedotin as a single agent in Chinese patients with relapsed/refractory CD30+ HL or sALCL. Brentuximab vedotin will be administered as a single, 1.8 mg/kg IV infusion on Day 1 of each 3-week cycle.

Patients will receive a maximum of 16 cycles if they do not meet the criteria for removal from the study. Patients will be assessed for overall response using the Revised Response Criteria for Malignant Lymphoma [1]. Dedicated computed tomography (CT) scans (neck, chest, abdomen, and pelvis) will be performed at Baseline and at Cycles 2, 4, 7, 10, 13, and 16, and positron emission tomography (PET) scans will be performed at Baseline and at Cycles 4 and 7. No additional PET scanning is required beyond Cycle 7 unless clinically indicated. B symptoms will be assessed at Baseline and on Day 1 of each cycle.

Patients may continue on study treatment until the sooner of disease progression, unacceptable toxicity, or completion of 16 cycles. Patients, including those who discontinue study treatment for any reason other than withdrawal of consent, will have safety follow-up assessments through 30 days after the last dose of study drug until end of treatment (EOT). Patients who discontinue study treatment with stable disease (SD) or better will be followed for PFS until disease progression, death, withdrawal of consent, or initiation of a new treatment other than the stem cell transplantation (SCT), whichever occurs first. A CT scan will be performed every 12 weeks for the first 12 months and at 18 months after EOT. Patients will be followed for OS every 12 weeks until death, withdrawal of consent, or study closure, whichever occurs first. All patients will have the opportunity to be followed for 18 months after EOT. The study will be closed when all patients enrolled have completed the required follow-up.

Toxicity will be evaluated according to the National Cancer Institute Common Terminology Criteria for Adverse Events (NCI CTCAE), version 4.03, effective 14 June 2010 [2]. Laboratory values, vital signs, and electrocardiograms (ECGs) will be obtained to evaluate the safety and tolerability of brentuximab vedotin. Serial blood samples for determination of the serum/plasma

concentration and immunogenicity of brentuximab vedotin will be obtained at prespecified time points as described in Table B in Appendix A of the Study Protocol.

## **5.0 ANALYSIS ENDPOINTS**

### **5.1 Primary Endpoints**

- ORR.
- Safety: AEs, assessments of clinical laboratory values, and vital sign measurements.

### **5.2 Secondary Endpoints**

- CR rate.
- DOR.
- PFS.
- OS.
- B symptom resolution rate.
- Maximum observed plasma concentration ( $C_{max}$ ).
- Time to reach  $C_{max}$  ( $T_{max}$ ).
- Area under the plasma concentration-time curve from time 0 to infinity ( $AUC_{\infty}$ ).
- Presence of antitherapeutic antibodies (ATA) and neutralizing antitherapeutic antibodies (nATA) to brentuximab vedotin.

## 6.0 DETERMINATION OF SAMPLE SIZE

The study will enroll approximately 30 evaluable patients, including approximately 22 patients with HL and approximately 8 patients with sALCL. For information purposes, the ORRs achieved in previous studies in relapsed/refractory HL and sALCL are referenced below.

**Table 6.a ORRs in the Global Pivotal Studies and the Japan Study**

ORR (CR+PR) by IRF (95% CI)	
Global Study SGN035-0003 (HL: n=102)	74.5 (64.9, 82.6)
Global Study SGN035-0004 (sALCL: n=58)	86.2 (74.6, 93.9)
Japan Study TB-BC010088 (HL: n=9)	66.7 (29.9, 92.5)
Japan Study TB-BC010088 (sALCL: n=5)	100 (54.9, 100)

Some observed response rates and the 95% exact CIs for 22 patients with HL and 8 patients with sALCL are summarized as follows.

**Table 6.b ORRs and the 95% Exact CIs for Various Number of Responses**

HL (n=22)			sALCL (n=8)		
Responses	ORR (%)	95% Exact CI	Responses	ORR (%)	95% Exact CI
8	36.4	(17.2 59.3)	4	50.0	(15.7 84.3)
9	40.9	(20.7 63.6)	5	62.5	(24.5 91.5)
10	45.5	(24.4 67.8)	6	75.0	(34.9 96.8)
11	50.0	(28.2 71.8)	7	87.5	(47.3 99.7)
12	54.5	(32.2 75.6)	8	100	(63.1 100.0)
13	59.1	(36.4 79.3)			

Based on the exact binomial CI calculations, a minimum of 9 responses observed from 22 evaluable patients with HL (ORR of 40.9%) will provide a 95% CI (20.7%, 63.6%); 5 responses observed from 8 evaluable patients with sALCL (ORR of 62.5%) will yield a 95% CI (24.5%, 91.5%). In both cases, the lower limits of the 95% CIs are greater than the threshold response rate of 20% obtained from the results of alternative therapies for the same indications.

Assume similar ORR results to those in the Japan Study TB-BC010088 will be obtained, eg, the expected response rates are 65% for HL and 80% for sALCL. With 22 patients with HL and 8 patients with sALCL, the study will have >99% and >94% probability, respectively, to observe an ORR such that the lower limit of its 95% exact CI is still greater than the 20% threshold (ie, observe  $\geq 9$  responses for HL and  $\geq 5$  responses for sALCL).

## 7.0 METHODS OF ANALYSIS AND PRESENTATION

### 7.1 General Principles

In general, descriptive statistics (number of observations, mean, standard deviation [StdDev], median, minimum, and maximum) will be used to summarize continuous variables. Frequency and percentage will be used to summarize categorical variables. Time-to-event data will be analyzed using the Kaplan-Meier method and results will be summarized by the 25th, 50th (median), and 75th percentiles, if estimable, with associated 2-sided 95% confidence intervals, as well as the percentage of censored observations.

Means and medians will be presented to 1 more decimal place than the recorded data. The standard deviations (StdDev) will be presented to 2 more decimal places than the recorded data. Confidence intervals about a parameter estimate will be presented using the same number of decimal places as the parameter estimate.

Unless otherwise specified, safety and efficacy data will be summarized in the following 3 groups: patients with r/r HL only, patients with r/r sALCL only, all patients. Analyses pertaining to pharmacokinetics and immunogenicity will be summarized by treatment cycle at the prespecified time points.

The baseline value is defined as the value collected at the time closest to, but prior to, the start of study drug administration, unless otherwise specified. A windowing convention may be used to determine the analysis value for a given study visit for observed data analyses.

All available efficacy and safety data will be included in data listings and tabulations. Data that are potentially spurious or erroneous will be examined under the auspices of standard data management operating procedures. In general, there will be no imputation of missing data. For time-related endpoints, subjects who have no specified events will be censored as specified for each respective endpoint in Section 7.8. Imputation rules for missing dates of AEs and concomitant medications are detailed in Sections 7.1.3 and 7.1.4.

The primary analysis for the clinical study report including the primary and the secondary endpoints will be conducted when all patients have had the opportunity to receive 16 cycles of treatment and have had EOT assessments. The results will be summarized in the primary CSR. The final analysis will be conducted when all patients have had the opportunity to be followed for 18 months after EOT. These results will be summarized in the CSR Addendum.

SAS Version 9.4 (or higher) will be used for all analyses.

#### 7.1.1 Definition of Study Days

Study Day 1 is defined as the date on which a subject is administered their first dose of the study medication. Other study days are defined relative to the Study Day 1 with Day 1 being Study Day 1 and Day -1 being the day prior to Study Day 1.

### 7.1.2 Definition of Study Visit Windows

All data will be categorized based on the scheduled visit at which it was collected. These visit designators are predefined values that appear as part of the visit tab in the eCRF.

### 7.1.3 Conventions for Missing Adverse Event Dates

Missing or partial AE start dates will be imputed according to the following rules.

**Table 7.a Imputation Rules for Missing AE Start Dates**

Non- missing	Missing	Estimated
Month and Year	Day	Day of first dose date of STUDY DRUG, if month and year of onset date are the same as month and year of date of first dose.  The last day of the month, if the month and year of onset date are before the month and year of date of first dose of STUDY DRUG.  The first day of the month, if the month and year of onset date are after the month and year of date of first dose of STUDY DRUG.
Year	Day and Month	Day and month of first dose date of STUDY DRUG, if the year of onset date is the same as the year of date of first dose of STUDY DRUG.  December 31st, if the year of onset date is prior to the year of date of first dose of STUDY DRUG.  January 1st, if the year of onset date is after the year of date of first dose of STUDY DRUG.
Day, Month and Year		Date of first dose of STUDY DRUG

Missing or partial AE stop dates will be imputed according to the following rules. If only the day is missing, use 15th of the month; if both month and day are missing, use June 30th. For a record with a complete start date and a partial stop date, if the estimated stop date would become earlier than the start date, the stop date will not be estimated.

If AE stop date is not missing and AE stop date < estimated start date, let estimated onset date = AE stop date.

All dates presented in listings are recorded dates without imputation.

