#### **4.1.5 Known or Potential Risks of Brentuximab Vedotin**

- Brentuximab vedotin treatment causes peripheral neuropathy, both sensory and motor. Brentuximab vedotin-induced peripheral neuropathy is typically cumulative and generally reversible. Monitoring patients for symptoms of neuropathy, such as hypoesthesia, hyperesthesia, paresthesia, discomfort, a burning sensation, and neuropathic pain or weakness, is required. Patients experiencing new or worsening peripheral neuropathy may require brentuximab vedotin dose modifications, including a dose delay (see [Table 9.a](#)).
- Complete blood counts should be monitored before each dose of brentuximab vedotin, and more frequent monitoring should be considered for patients with Grade 3 or 4 neutropenia. Prolonged ( $\geq 1$  week) severe neutropenia can occur. If Grade 3 or 4 neutropenia develops, manage with dose delays, reductions, or discontinuations (see [Table 9.a](#)).
- Infusion-related reactions, including anaphylaxis, have occurred with brentuximab vedotin. Monitoring of patients during infusion is required. If anaphylaxis occurs, the administration of brentuximab vedotin should be immediately and permanently discontinued and appropriate medical therapy administered. Patients who have experienced a prior infusion-related reaction should be premedicated according to institutional guidelines for subsequent infusions. Premedication may include acetaminophen, an antihistamine, and a corticosteroid.

- Any treatment that can decrease immune function may contribute to malignancy and infections; patients are to be monitored for these events during the treatment period and up to and including 30 days after the last dose.
- Stevens-Johnson syndrome (SJS)/toxic epidermal necrolysis (TEN) have been reported with brentuximab vedotin. If SJS/TEN occurs, brentuximab vedotin must be discontinued and the appropriate medical therapy administered.
- Tumor lysis syndrome may occur. Patients with rapidly proliferating tumors and high tumor burden are at risk of tumor lysis syndrome and should be closely monitored. If tumor lysis syndrome occurs, take medically appropriate measures.
- Progressive multifocal leukoencephalopathy (PML) has been reported with brentuximab vedotin use. If PML is suspected, a diagnostic work-up should be performed as described in Section 9.6.5.

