### 7.11.1 Adverse Events

AEs will be tabulated according to the Medical Dictionary for Regulatory Activities (MedDRA) Version 19.0 or higher by system organ class, high-level terms, preferred terms and severity. AEs with missing start and/or end dates will be imputed according to rules specified in Section 7.1.3. TEAEs are defined as any AEs that occur after administration of the first dose of brentuximab vedotin and up through 30 days after the last dose. Patients who experience the same AE more than once will have that event counted only once within each system organ class, once within each high-level term, and once for each preferred term. AEs will be summarized and will include the following categories:

- TEAEs.
- Drug-related TEAEs.
- Grade 3 or higher TEAEs.
- Grade 3 or higher drug-related TEAEs.
- TEAEs resulting in study drug discontinuation.
- SAEs.
- AEs of peripheral neuropathy identified by the broad search MedDRA SMQ “Peripheral neuropathy”.

Treatment-emergent AEs will be tabulated by system organ class, high-level term and preferred term. The most commonly reported treatment-emergent AEs (ie, those events reported by ≥10% of all patients) will be tabulated by preferred term. Additional analyses of peripheral neuropathy may also be presented.

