#### *7.11.1.2 Peripheral Neuropathies*

Peripheral Neuropathy (PN) is defined by the peripheral neuropathy SMQ broad search. The incidence of treatment-emergent PN and treatment-emergent drug-related PN will each be summarized by preferred term and severity. The incidence of peripheral motor neuropathy will also be calculated. Time to onset, resolution and improvement of PN events will be summarized. Individual plot by preferred term for treatment-emergent peripheral neuropathy (SMQ) may be presented.

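### Partial AE start dates that could be on treatment are set to the earliest on-treatment day, and the SAP gives neuropathy timing no date rule of its own, so onset is biased early for affected events

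*SAP*

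**What the plan says.** SAP 7.1.3, Table 7.a, has seven branches for an incomplete AE start date.

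| Known part of the date | Relative to first dose | Imputed start |
|---|---|---|
| Month and year | Same month | First-dose date: "Day of first dose date of STUDY DRUG, if month and year of onset date are the same as month and year" |
| Month and year | Later | Start of the month: "The first day of the month, if the month and year of onset date are after the month and year" |
| Month and year | Earlier | End of the month: "The last day of the month, if the month and year of onset date are before the month and year" |
| Year | Same year | First-dose date: "Day and month of first dose date of STUDY DRUG, if the year of onset date is the same as the year" |
| Year | Later | 1 January |
| Year | Earlier | Year end: "December 31st, if the year of onset date is prior to the year of date of first dose of STUDY DRUG" |
| Nothing | Unknown | First-dose date |

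Two further rules follow the table. An imputed onset is moved back to the stop date if the stop date is earlier. Partial stop dates become the 15th of the month or 30 June. Listings show recorded dates only.

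SAP 7.11.1 then states "AEs with missing start and/or end dates will be imputed according to rules specified in Section 7.1.3", with no limit on the purpose. Its subsection 7.11.1.2 states "Time to onset, resolution and improvement of PN events will be summarized", with no formula, start point or date rule.

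**The concern.** The earliest-date convention is a deliberate worst case for one question: should this event count as treatment-emergent? Used to measure when an event began, the same convention errs in one direction, and the errors do not average out across patients.

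Protocol 4.1.5 says that this drug's "peripheral neuropathy is typically cumulative and generally reversible". Onset time and recovery time are how those two properties are described in the report. An imputed onset on the day of the first infusion works against the first property. A lengthened onset-to-resolution interval works against the second.

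**Working it through.** The plan states no figure on this point, so there is none to reproduce. The check has four steps.

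**1. Do these dates reach the neuropathy summaries?** SAP 7.1 says missing data are generally not imputed and names 7.1.3 as the rule for AE dates. SAP 7.11.1 applies 7.1.3 to AEs with missing dates. SAP 7.11.1.2 sits under 7.11.1 and offers nothing else. The link is therefore an inference, but no other reading is offered.

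**2. Error in onset.** Error = true onset minus imputed onset.
- Day missing: at most 31 − 1 = 30 days early.
- Day and month missing: at most 365 − 1 = 364 days early in an ordinary year (first dose 1 January, onset 31 December). With no dosing delays, the sixteenth dose falls 15 × 21 = 315 days after the first, and the 30-day window closes at 315 + 30 = 345 days. For treatment-emergent events the full 364 therefore needs delayed cycles, which the protocol allows.
- Wholly missing: onset is always Day 1, so the error is the whole true time to onset.

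Example: first dose 10 March, true onset 20 October, which is Day 225. With month and year known, onset becomes 1 October (Day 206), 225 − 206 = 19 days early. With only the year known, it becomes Day 1, 224 days early.

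A simulation of the rules (50,000 draws per case) gives typical sizes. Assumptions: first dose uniform over a calendar year, and true onset uniform over the first 126, 252 or 366 days. No imputed start was later than the true start.

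| Missing part | Mean days early (126 / 252 / 366-day window) | Share set to first dose |
|---|---|---|
| Day | 13.4 / 14.1 / 14.2 | 12% / 6% / 4% |
| Day and month | 55 / 97 / 122 | 83% / 66% / 50% |
| All | 62 / 126 / 182 | 100% |

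**3. Error in onset-to-resolution.** This step assumes that resolution time is counted from onset, which the SAP does not say. If it were counted from first dose, the start-date rule would not affect it. Further assumptions: the 366-day onset window, true durations of 14, 60 or 180 days, and the stop-date override also applied to imputed stop dates.

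| Start missing | Stop date | Mean error (days) | Share too short |
|---|---|---|---|
| Day | Complete | about +14 | 0% |
| Day and month | Complete | about +121 | 0% |
| Day | Day missing | about +14 | 1% to 9% |
| Day | Year only | +12 to +46 | 43% to 47% |
| Day and month | Year only | +119 to +125 | 12% to 13% |

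With a complete stop date the duration is never understated. With a partial one the mean error stays positive in these cases, but the sign for a single event is not fixed.

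**4. How many events are involved?** Protocol 4.1.4 reports peripheral sensory neuropathy in 44% of patients in the earlier phase 2 studies. If that rate applied here, 0.44 × 30 ≈ 13 patients would have an event, of whom 0.44 × 8 ≈ 3.5 would be in the sALCL group, which SAP 7.1 summarises separately by default. With three events, setting either of the two later onsets to Day 1 moves the median to what was the earliest onset.

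**The case against.** The strongest reply is that partial neuropathy dates should be rare. Patients are seen on Days 1, 8 and 15 of the first two cycles and on Days 1 and 15 of later ones. Protocol 9.6.4 and 10.3.13 require detailed tracking of neuropathy severity, and 13.1 provides logic checks and site queries for missing or inconsistent dates. If only days are ever missing, the effect is slight. One illustration assumed 14 events, a true median onset of about 103 days and 20% of dates lacking the day; the median onset fell by about 3% and onset-to-resolution rose by about 5%. Adding 10% year-only dates moved the median onset from 103 to 92 days. Under that model the standard error of the median is roughly 1.253 × 0.7 / √14 = 0.23 on the log scale, or about 23 days, so even the 11-day shift is under half a standard error. The timing summaries are also descriptive, are not a named endpoint, and come after incidence tables that the rule serves well. Listings leave incomplete dates visible.

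All of this stands, and it is why the priority is minor. It does not remove the point: the shift is systematic, unlike sampling error, and one sentence would prevent it.

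Three stronger readings are tempting, and the documents do not support them.
- A reader might infer that Table 7.a always uses the earliest on-treatment day. Two branches give the latest pretreatment day, and the stop-date override can move an imputed onset.
- A reader might infer that the SAP expressly prescribes imputed dates for neuropathy timing. It is silent; the use follows from 7.11.1.
- A reader might infer that durations are always too long. That is assured only with a complete stop date.

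**Conclusion.** The point holds for partial or missing start dates that could be on treatment. Following the SAP as written, neuropathy onset for those events is early by up to 30 days (day missing), up to 364 days (day and month missing), or placed on Day 1 (wholly missing). Onset-to-resolution is overstated or at best unchanged where the stop date is complete; otherwise the direction for an individual event is open. This rests on reading 7.11.1 as governing 7.11.1.2 and, for resolution, on counting from onset.

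No overall percentage can be given. It depends on the share of partial neuropathy dates, which the documents do not state and which close follow-up may keep small. The treatment-emergent classification and the incidence tables are not in question. Minor priority; a cheap improvement.

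**What to change.** Add to the SAP:
- Start dates imputed by Table 7.a are used only to classify AEs as treatment-emergent.
- For neuropathy timing, if only the day is missing, use the midpoint of the feasible days in that month, bounded by first dose and any known stop date. In the example above, 1 to 31 October gives 16 October, 4 days from the true date instead of 19. In a 31-day month with no other bound, the largest error falls from 30 to 15 days.
- If the month or the whole date is missing, leave the event out of the timing summaries, report how many were left out, and keep it in every incidence table.

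A timing summary restricted to recorded complete dates is an acceptable alternative.

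The cost is a few SAP sentences and one derived variable. The downside is that a few events leave a descriptive summary, and those left out may not be typical, which is why their number should be shown. The midpoint is itself an assumption, but it does not push every date the same way.
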